Psychiatrists will fill out the comprehensive Physician's Report Form ([name], [name], et al., 2020) at each study pharmacotherapy visit. The form records the current medication regimen and dosages, dosage modifications or medication switches since the previous visit, reasons for these switches symptoms during the previous 2 weeks, suicidal ideation or behavior, adverse events. This form, which has evolved over the past 10 years to track a variety of information important to clinical decision-making, includes physician-rated Clinical Global Impression – Bipolar Disorder (CGI-BP; Spearing et al., 1997) and Child's Global Assessment Scale (CGAS; Shaffer et al., 1983) ratings. The CGI-BP rates current depressive, manic, and overall bipolar symptoms on a 1 (normal) to 7 (extremely ill) point scale, and the CGAS uses a 1-100 scale of functioning.

Data from the Physician's Report Form will be important to the guideline adherence scores made by the Pharmacotherapy Oversight Committee. The Committee will measure the adherence of physicians in implementing the protocol based on ratings of each study visit on a 1 (nonadherent), 2 (partially adherent) or 3 (fully adherent) scale. Our prior studies of bipolar adolescents and adults have found that study psychiatrists can remain adherent to a protocol algorithm with regular supervision from experts, with little drift across time (e.g., [name] et al., 2014).

9.i. Pharmacological Treatment of Acute Illness Episodes

If a child shows a clinically significant elevation of mood disorder symptoms at any time during the study (i.e., a sudden worsening of mood or behavior), study psychiatrists will introduce emergency prophylactic medication as clinically indicated to forestall the development of a syndromal mood episode. If the child is not taking mood stabilizing or atypical antipsychotic

medications, these agents will be introduced; if the child is already taking medications, these agents will be augmented with other agents, or dosages will be increased. Thus, there will be no delays in the initiation of rescue pharmacotherapy when a child's mood worsens.

If a study youth shows the early warning signs of mania (e.g., decreased need for sleep, irritable or elevated mood, grandiose thinking) or begins to sink into depression (pessimistic thoughts, decreased energy, insomnia), the independent research evaluator will notify the treating psychiatrist immediately, who will institute appropriate changes to the medication regimen (or initiate new medications) as per good clinical practice. When there are questions or difficult cases, psychiatrists will consult with the pharmacotherapy oversight team to determine how to modify drug treatments in the most clinically appropriate manner. Typically, changes will include adding a second mood stabilizer or an atypical antipsychotic agent.

Family members will be instructed to notify their assigned psychiatrist and case coordinator if they observe sudden deteriorations in the mood or behavior of the child at home or in the school setting. When clinically appropriate, psychiatrists will instruct the family as to how to get the youth to the nearest hospital emergency room. The clinicians will facilitate communication between the family and the hospital. In all cases, they will re-contact the family within 24 hours to be sure that contact has been made with the appropriate care provider.

Parents or siblings of the youth may also require referral for pharmacological treatment. For example, a parent with bipolar I disorder may have a recurrence and require initiation of pharmacotherapy or a reevaluation of their regimen. In all cases, we will refer relatives to an appropriate clinical provider and obtain ongoing information on their treatment regimen, using the Treatment Utilization Form ([name] et al., 2020), administered at each follow-up visit.

9.j. Preventing Suicidal Episodes

Children with or at risk for bipolar disorder are at heightened risk for suicide (Goldstein et al., 2005). Special precautions will be undertaken to prevent the onset of suicidal crises. We will learn of new onsets of suicidal ideation or new attempts because we will have regular contacts with children and parents (a minimum of once monthly). Information about suicidal ideation will be obtained by the psychiatrist during the psychopharmacology sessions, by weekly online parent reports, and by the research assessor in face-to-face assessments. The project coordinator

and assessors will contact the study psychiatrist and PI if mood deteriorations are detected so that rescue medications or crisis counseling can be introduced.

When a participant (an at-risk youth or a family member) expresses suicidal thoughts, the treating psychiatrist will conduct a thorough lethality and safety assessment with the relevant person and arrange hospitalization if necessary. Rescue medications will be introduced by the psychiatrist as medically appropriate. The participant will be referred for evaluation at the hospital emergency room if the treating psychiatrist cannot be reached.

If the suicide risk is deemed low, the treating psychiatrist will intervene to prevent escalation of the suicidal thoughts or behaviors. This will usually include additional psychiatric sessions for the child and/or family. Addressing suicidality usually includes (a) conducting chain analyses to assess the precipitants and consequences of suicidal thoughts or actions, (b) providing training in distress tolerance skills (e.g., deep breathing for anxiety); (c) developing a suicide prevention contract (i.e., identifying triggers for suicidal thoughts; lists of who the child or adult will call if he or she feels suicidal; how the parents can get in touch with the psychiatrist or therapist and what to do if they are unavailable); (d) enhancing family communication focused on supportive interactions that encourage the family members' expressions of compassion and concern, and (e) problem-solving to eliminate triggers of suicidal thoughts and prevent the escalation of suicidality.

9.k. Availability of Alternative Non-Protocol Treatments

We will explain to participants that, instead of receiving psychiatric treatment from a study psychiatrist, the youth may initiate or continue medication treatment with his/her existing psychiatrist or primary care physician. If the family so chooses, the study psychiatrist will assemble a report detailing his or her evaluation of the child and send it to the family's chosen physician. It will be up to the primary care physician and family to determine whether or not to follow these recommendations.

Participants who have recurrences of their illness may require emergency services. A child who needs to be hospitalized (e.g., for suicidality) will be reentered into the study after hospital discharge if the child and parents agree to continue participating.

Because bipolar disorder runs in families, one or more of the child's relatives may have bipolar I or II disorders themselves, or other mood, substance, or anxiety disorders. Parents with BD will have been identified on the basis of the Family History screen, as well as via spontaneous self-report during the evaluation or treatment sessions. If family members request ancillary treatment for themselves or another relative, or if in the psychiatrist's or family clinician's judgment referral to an outside therapist or physician is clinically indicated, we will refer the relative to the appropriate care providers, including referrals for pharmacotherapy evaluations as needed. If family members require hospitalization, we will follow the same advocacy procedures described above for the symptomatic child participant.

Family members of the youth (parents or siblings) can pursue ancillary treatments without jeopardizing the family's involvement in the study. Thus, participants or family members may take part in individual therapy, support groups, chemical dependency programs (such as A.A.), or domestic violence prevention programs without being terminated from the study. If parents would like to join a multifamily group, they may do so without jeopardizing their involvement in the study.

9.I. Protocol to Maximize Retention of Study Subjects

We will make every attempt to retain all participants in the longitudinal protocol for as long as possible. We have found that retention hinges on maintaining excellent rapport with children and parents, communicating optimism and hopefulness, and fostering the attitude that every participant is important. Relatedly, it is essential to get to know each member of the family as a person and emphasize personal strengths.

On a practical level, retention requires obtaining telephone numbers, addresses, and email addresses for participants and their parents, including parents' cell phone numbers and workplace numbers. This information must be repeatedly updated throughout the study. We will retain contact with participants who are difficult to reach unless the participant has stated that he/she (or the parent) no longer wants to participate and no longer wishes to be contacted. In cases where a participant declines a research interview or family session, we will ask permission to recontact him/her in the near future. With the participants' permission, we will obtain contact information for grandparents and other extended family members so that we can locate the family if the contact information we have is no longer valid.

The following procedures have also helped us to maximize retention: (1) be flexible about the time of day that assessment or treatment sessions are offered (i.e., after school, early evening, weekends); (2) sending birthday and holidays cards to the child and parents; if the cards are returned because of a wrong address, immediately track the new address; (3) check in with participants about their goals and expectations early in treatment, and revisit these goals from time to time to make sure they are being addressed; (4) provide appointment reminder cards; (5) offer between-session phone consultations as needed; (6) offer the parents or the child extra support as needed through additional therapy sessions, (7) serve as a source of treatment or medical referrals for the family; (8) remunerate children and parents for completing each follow-up interview and questionnaire battery, with compensation divided evenly between them.

9.m. Circumstances That May Require Study Withdrawal

Noncompliance. Participants will be withdrawn from the protocol if they are noncompliant with the study procedures (for example, refuse the research assessment interviews). Participants will not be dropped from the protocol if they are noncompliant with their medication regimens. The circumstances that may require administrative withdrawal will be spelled out in the consent forms.

Substance or alcohol abuse. The Drug Use Screening Inventory, Revised (DUSI-R; Tarter 1990), a self-report questionnaire, will be administered to supplement the MINI substance abuse module at baseline and follow-ups, covering the prior month. Scores reflect gradations of severity and frequency of use of alcohol and substances. If the child shows evidence of regular substance or alcohol use during the study protocol, has a positive toxicology screen, and/or develops a DSM-5 substance/alcohol abuse or dependence disorder, we will retain him or her in the protocol for as long as possible and work toward abstinence. In most cases involving significant substance or alcohol abuse, we will make referrals for adjunctive chemical dependency treatment. We will make this determination on a case-by-case basis as medically or ethically appropriate. Referrals can include age-appropriate modified 12-step programs with psychiatric oversight, drug rehabilitation facilities, and various forms of individual treatment (i.e., motivational enhancement, cognitive-behavior therapy). Study staff members will follow-

up to assure that the youth and family have pursued adjunctive treatment. Adjunctive chemical dependency treatment will not preclude continued participation in the study protocol.

If the child is using alcohol or drugs regularly and (a) psychiatric treatment is jeopardized (for example, the child comes to sessions intoxicated, cannot function during sessions, consistently no-shows) and (b) refuses adjunctive substance or alcohol abuse counseling or other chemical dependency treatment, we will inform the child and parents that the substance use must stop or the child will be discontinued from the study. We will continue to monitor the child's clinical status and substance abuse behavior for the next 4 weeks. If the child continues to meet DSM-IV substance abuse/dependence criteria (i.e., persistent use) and is unable to participate in treatment, he or she will be discontinued from the study. In all cases, children will be referred to the appropriate substance abuse treatment clinic. In our previous studies, we have not had to withdraw any subjects due to persistent substance abuse.

Participants will be informed of these rules during the recruitment phase of the study, both through information given orally and via our informed consent procedures. We will make clear that discontinuing participation in the study will in no way jeopardize their access to other treatments. Thus, they can have regular pharmacotherapy or psychotherapy at the relevant study outpatient clinic even if no longer participating in the study. Whenever possible, we will continue to follow these children using the research outcome battery so that they can be included in intent-to-treat analyses. We will record the nature of the adjunctive drug/alcohol treatment services received (i.e., number of sessions, frequency, and costs) using the *Treatment Utilization Form*.

9.n. Tolerability of the Baseline and Follow-up Assessment Batteries

Our prior experience with assessment batteries similar to the one proposed for this study has been that they are well-tolerated by children and adults. We estimate that the initial assessment battery (i.e., KSADS, MINI, questionnaires) will require approximately 2-3 hours from the parent and the youth, which can be spread over two sessions. The follow-up interview and questionnaire battery currently averages 1.0-1.5 hours every 6 months.

The research personnel are trained to be attentive to fatigue, especially when the child is actively symptomatic. Where appropriate, the interviewer will subdivide the assessments across

two or more sessions to decrease the participants' fatigue and assure the integrity of the data. Children will be allowed to take breaks as often as they require.

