connected through the UCLA VPN from an offsite location. Data transferred using devices (such as USB drives and laptops) will be encrypted following UCLA Health device encryption policies. Storage and access procedures are in full compliance with UCLA Health data security policies.

Our primary analytical techniques will be generalized linear mixed models (GLMMs) and survival analyses, run on an intent-to-treat basis. GLMMs estimate a slope and intercept for each individual and can handle missing data on key outcome variables. Our primary outcomes are symptom severity (i.e., the 1-6 ALIFE Psychiatric Status Ratings) and secondary are remission or recurrence (also recorded on the A-LIFE). The GLMM and survival models will be fit initially without covariates, following standard practices (Kraemer, 2015). We will use logistic regression to identify factors associated with attrition and data loss, and control for these factors in sensitivity analyses. We will protect against multiple comparisons by focusing on a limited set of a priori primary outcomes and contrasts and by reporting results within each hypothesis using false discovery rate procedures (Hochberg & Benjamini, 1990).

For example, when examining the association between study sites and study outcomes, we will code site as a between-subjects variable, symptoms (for example, ALIFE Psychiatric Status Ratings of depression) as the dependent variable, and study visit (baseline, 6 months, or 12 months) as the repeated time variable. These models will examine site by time interactions. There will be subject level random effects to account for individual variation in response trajectories. Covariates may include the child's sex, diagnostic status (bipolar I, II or OSBD), race, ethnicity, or socioeconomic status.

Secondary analyses will concern repeated dependent variables (e.g., parent POWERS ratings) computed from all relevant information at each time point, including information gathered through the MyCoachConnect mobile app. We will determine the degree to which inflammatory variables are associated with changes in symptom severity over 12 months. The correlations between data collected through MyCoachConnect and data collected through interviews and questionnaires will be examined using mixed effect regression models. Using all available variables, we will compute a clinical forecasting model consisting of inflammatory variables at baseline as predictors of symptoms at 0, 6, and 12 months.

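### Protocol 9.m withdraws youth who refuse research interviews while 9.l seeks to recontact them, and nothing says which rule applies when

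*Protocol*

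**What the plan says.** Four places in the protocol bear on a youth who will not do a research interview.

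- **Section 9.l (retention).** The stated aim is broad: "We will make every attempt to retain all participants in the longitudinal protocol for as long as possible". For a refused interview the step is specific: "In cases where a participant declines a research interview or family session, we will ask permission to recontact him/her in the near future". For families who are hard to reach, contact ends only on their own statement: "We will retain contact with participants who are difficult to reach unless the participant has stated that he/she (or the parent) no longer wants to" take part or be contacted.
- **Section 9.m, noncompliance paragraph.** "Participants will be withdrawn from the protocol if they are noncompliant with the study procedures (for example, refuse the research assessment interviews"). The wording is mandatory, and refusing the interviews is the only example given. The same paragraph says that not taking medication does not lead to withdrawal, and that the grounds for administrative withdrawal will appear in the consent forms.
- **Section 9.m, closing paragraph.** After the substance-use rule, the protocol says that, where feasible, "we will continue to follow these children using the research outcome battery so that they can be included in intent-to-treat analyses".
- **Section 7 (Data Analyses).** "Our primary analytical techniques will be generalized linear mixed models (GLMMs) and survival analyses, run on an intent-to-treat basis". The same section says that the mixed models can accommodate missing outcomes. It also plans a logistic model for attrition and data loss, with sensitivity analyses that control for the factors found.

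**The concern.** Sections 9.l and 9.m prescribe different responses to what may be the same event. A coordinator facing a youth who refuses the 6-month interview can follow either section and be within protocol. Four sites could settle on four practices, while section 7 plans to test site-by-time interactions.

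The stake is the primary outcome. The weekly Psychiatric Status Ratings come from the A-LIFE interview (section 5.i.1), and there are only two follow-up interviews, at 6 and 12 months. Withdrawal at the first refusal also ends the 12-month interview, which a family might have accepted. The A-LIFE and several questionnaires are also taken from a parent, so withdrawal can silence an informant who did not refuse.

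The closing paragraph of 9.m shows that the sponsor wants outcome data after discontinuation, but it is not clearly written for this group.

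**Working it through.** **Step 1. The two rules side by side.**

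| Question | 9.l | 9.m, noncompliance |
|---|---|---|
| Trigger | Declines an interview (singular) | Refuses the interviews (plural), as an example of noncompliance |
| Response | Ask permission to recontact | Withdrawal, stated as mandatory |
| Number of refusals | Not stated | Not stated |
| Time window or order of steps | Not stated | Not stated |
| What ends contact | The family's own statement (given for hard-to-reach families) | The refusal itself |

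The heading of 9.m, "Circumstances That May Require Study Withdrawal", speaks of what may happen, whereas its text speaks of what will.

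**Step 2. Scope of the continued follow-up.** The closing paragraph of 9.m comes straight after the substance-use rule, and its next sentence concerns drug and alcohol services. Its opening, however, refers to the withdrawal rules in general. Either scope can be read into it.

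**Step 3. What one refusal costs.** Each follow-up A-LIFE rates the preceding 6 months, so two interviews cover 2 × 26 = 52 weeks. For a youth who refuses at 6 months but would accept at 12:

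- Recontact, with the next battery offered: months 7-12 are rated, 26 of 52 weeks. Section 7's model has 2 of its 3 visits (baseline, 12 months).
- Withdrawal at first refusal: 0 of 52 weeks, and 1 of 3 visits (baseline only).

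The difference is 26 weeks per youth. The gain is smaller for recovery and recurrence, because events in months 1-6 stay unobserved unless recontact yields a late interview.

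**Step 4. The plan's own attrition figure.** Section 5.c expects 80% of those consenting to complete and wants 20 completers per site. 20 / (1 − 0.20) = 25 per site, which matches. Over four sites, 4 × 25 = 100 enrolled and 100 × 0.80 = 80 completers. The 20% loss covers all causes, including youth found ineligible after consent.

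**Step 5. Illustration on assumed rates only.** The protocol gives no refusal rate. Let r be the share refusing at 6 months, p the share of these who would accept at 12 months, and q = r × p the extra permanent loss if withdrawal follows the first refusal. Completers per 100 are 100 × (0.80 − q), and recruitment per site is 20 / (0.80 − q), rounded up.

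| r (assumed) | p (assumed) | q | Completers per 100 | Recruit per site |
|---|---|---|---|---|
| 0.05 | 0.30 | 0.015 | 78.5 | 25.5 → 26 |
| 0.10 | 0.50 | 0.05 | 75 | 26.7 → 27 |
| 0.20 | 0.70 | 0.14 | 66 | 30.3 → 31 |

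This treats q as additional to the 20%. If the past studies behind the 80% worked under a similar rule, some or all of q is already in it.

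**Step 6. When the loss would bias.** If a fraction f is lost and their mean 12-month rating exceeds that of the rest by d points, an unadjusted completer mean is too low by f × d. With f from 0.05 to 0.20 and d from 0 to 1.5 (both assumed), this runs from 0 to 0.20 × 1.5 = 0.30 points. At d = 0 it is zero whatever f is, so the rule creates missing data but does not by itself make it informative.

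**The case against.** The best defence is a stepwise reading: one declined interview leads to recontact, and sustained refusal of all interviews leads to administrative withdrawal. The singular in 9.l, the plural in 9.m, the softer heading and the retention aim all fit it. The consent forms, which are to list the grounds for withdrawal, may state a threshold; they are not among the pages available. This reading is possible, and closing the file of someone who persistently refuses every interview is not an error. But the protocol does not state it, and with two follow-up interviews one refusal is already half of them.

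A reader might infer that the rule contradicts the analysis being "run on an intent-to-treat basis". The protocol does not support that. Nothing is randomized, so no allocation comparison is broken. Withdrawal does not delete data already collected, and the mixed models use partial records. What stands is narrower: the provision for continued follow-up is not clearly extended to noncompliance cases.

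A reader might also infer that the rule makes later missing data informative. No section links refusal to mood state. A link is plausible in this population but not shown, and section 7 already plans an attrition model. That model can adjust only for observed factors, so it does not replace interviews that could have been obtained.

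It is also fair that a youth who refuses the interview refuses the very battery that continued follow-up would use. That limits the benefit to those who would accept later, or whose parent would.

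**Conclusion.** The point holds as an unreconciled pair of instructions with an avoidable cost. Section 9.m states a mandatory withdrawal rule, 9.l states a recontact rule for a declined interview, and nothing marks where one gives way to the other. The reach of the continued outcome follow-up in 9.m is ambiguous for the same youth.

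Per affected youth, the loss is 26 of 52 follow-up weeks of the primary outcome, if withdrawal follows a refused 6-month interview and the 12-month one would have been accepted. The number affected cannot be derived from the protocol. The range of 1.5 to 14 per 100 rests wholly on the assumed refusal and return rates, on withdrawal at the first refusal, and on everyone enrolled being eligible for follow-up. Its upper end assumes a refusal rate at one visit as large as the whole 20% allowance for all causes. Bias is a possibility, not a finding. The matter should be put right because the remedy is nearly free; it does not invalidate the planned analyses.

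**What to change.** Reconcile 9.l and 9.m in one amendment:

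1. In 9.m, remove refusal of a research interview as a ground for mandatory withdrawal and record it as a missed visit with the reason.
2. Refer to the recontact step in 9.l, and state that the next scheduled battery is still offered, including the parent's part if only the youth refuses.
3. State that research data collection ends only when the family withdraws consent or asks not to be contacted.
4. State that the continued outcome follow-up at the end of 9.m also covers noncompliance cases.
5. Match the consent wording, since 9.m places these grounds there.

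If the sponsor prefers to keep administrative withdrawal for sustained refusal, the minimum is to state how many refusals, over what period and after which recontact attempts.

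The cost is a few sentences in the protocol and consent forms, plus a little coordinator time for recontact that 9.l already plans. Design, measures and analysis models stay as they are.
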